Platelet-rich plasma (PRP) is an autologous solution of human plasma with a high concentration of platelets. Platelet-rich plasma contains various growth factors that enhance the healing process and regeneration by initiating the stages of cell proliferation, differentiation, angiogenesis, and chemotaxis. The rationale for use and therapeutic potential of a high concentration of platelets is based on their capacity to supply supraphysiologic amounts of essential growth factors and cytokines which then provide a regenerative stimulus, promoting tissue repair [8]. Important growth factors released from platelets during the healing process include platelet-derived growth factor (PDGF), transforming growth factor (TGF- β), vascular endothelial growth factor (VEGF), epidermal growth factor (EGF), basic fibroblast growth factor (bFGF), and insulin-like growth factor (IGF-1) [9].

PRP has been described for the treatment of various health conditions, from hair loss to joint injuries. PRP is most studied and used for the treatment of musculoskeletal soft tissue injuries, including tendinopathies and tendon tears, and ligament, muscle, and cartilage injuries [10]. The injection of PRP is not a new technology, but it has not been well-studied in the field of urogynecology. Two small series have reported on use of PRP

for the treatment of female SUI, suggesting successful treatment outcomes in up to 80% of patients [11] [12]. With this study, we will provide higher quality evidence on the use of PRP in the treatment of SUI.

This study will aim to determine the 6-month post-treatment efficacy of PRP injection in the treatment of **SUI.** Knowledge gained from this study has the power to change clinical practice by equipping physicians with a minimally invasive and likely low risk SUI treatment.

Approach

The primary aims of this study are to determine the efficacy and safety of PRP injection into the anterior vaginal wall for the treatment of SUI.

The primary efficacy aim will be determined by the following outcome measures:

- 1. Negative urinary stress test (no leakage noted on examination during cough or Valsalva maneuvers at a standardized bladder volume of 300 mL [13]
- 2. Subjective outcome with improvement in the Patient Global Impression of Improvement (PGI-I), with positive response defined as "very much better" (1) or "much better" (2). [14]

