Treatment "success" will be defined as a negative CST and a reported PGI-I of "very much better" or "much better" 6 months after treatment.

The primary safety aim will be assessed by monitoring adverse events classified by the Clavien-Dindo Classification.

Secondary Outcomes that will be compared between groups include:

- 1. Female Sexual Function Index (FSFI) scores
- 2. Incontinence-Quality of Life (I-QOL) scores
- 3. Perception of Monetary Value
- 4. Questionnaire for Urinary Incontinence Diagnosis (QUID)
- 5. Visual Analog Scale (VAS) for patient pain/discomfort
- 6. Visual Analog Scale (VAS) for procedure difficulty (by provider)

Eligibility Criteria

- 1. Women aged 18 years or older
- 2. Pure or stress-predominant urinary incontinence with the Medical, Epidemiologic, and Social Aspects of Aging questionnaire (MESA) stress incontinence symptom score greater than MESA urge incontinence symptom score
- 3. Observation of leakage by provocative stress test at bladder volume \leq 300 mL [15]
- 4. Post void residual < 150 mL

Exclusion criteria

- 1. Currently pregnant or trying to conceive
- 2. Currently breastfeeding
- 3. Interstitial cystitis

- 4. Urgency urinary incontinence predominance or currently being treated for overactive bladder with medication, percutaneous tibial nerve stimulation, bladder chemodenervation, or sacral neuromodulation
- 5. Currently being treated for a sexually transmitted disease
- 6. Pelvic organ prolapse greater than stage 2 according to the Pelvic Organ Prolapse Quantification System
- 7. Periurethral mass
- 8. Active gynecologic, urologic or colorectal cancer
- 9. Any history of cancer within the last 5 years
- 10. Mental disorder making the patient unable to provide consent
- 11. Undiagnosed abnormal uterine bleeding
- 12. Genitourinary fistula
- 13. Prior SUI surgery
- 14. Use of anti-platelet or anti-coagulant medication
- 15. Use of non-steroidal anti-inflammatories
- 16. Regular use of non-steroidal anti-inflammatories

Methodology

This is a single-blind prospective randomized controlled trial comparing the efficacy of injection of 5 mL PRP into the anterior vaginal wall versus injection of 5 mL injectable saline for the treatment of SUI in females.

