At baseline and at time points of 1 month, 3 months, and 6 months, subjects will complete the previously described validated questionnaires (see visit details below). At a 1-month telephone visit, a subset of the questionnaires will be administered, and patients will be queried about any adverse events. At baseline and at time points of 3 and 6 months, all validated questionnaires will be completed, as well as a pelvic exam with a urinary stress test, performed by a nurse practitioner specifically trained in urogynecology, and who did not perform the injections and thus blinded to the randomization. All adverse events will be recorded and classified per the Clavien-Dindo Classification.

Figure 1. Location and Depth of Injections¹²

At the end of the 6 months, subjects will be unblinded.

If subjects have symptoms of SUI which are refractory to treatment with PRP they will be referred to Urology or Urogynecology and will be offered standard of care following completion of the final study visit. If patients wish to receive alternative treatment for SUI prior to completion of 6-month follow-up they will be exited from the trial and final outcomes will be assessed at that time

Subjects will be provided a \$50 eVoucher upon completion of the 6-month follow-up visit.

Data will be stored in a secure REDCap database, only accessible to the research team members. Randomization envelopes and the Randomization Log will be kept in a locked cabinet.

Power Analysis

Sample size calculations were performed based on a desired power of at least 90% and assuming true response rates of 70% and 20% for treatment and placebo groups, respectively. The 70% response rate in the active PRP treatment group was chosen based on prior studies of PRP, as well as urethral bulking procedures [12] [16] [17]. The response rate of 20% in the placebo arm was chosen based on prior urethral bulking studies showing a 20% rate of negative CST after placebo [18]. Using an unadjusted alpha of 0.05, a sample of 38 subjects (19 per treatment group) is the minimum number required to have >90% power to detect a difference between the response rates of the two treatments.

In order to account for a 20% drop-out rate, we will plan to enroll a total of 50 patients (25 per treatment group).

Statistical Analysis and Data Reporting

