For this study we will assess the demographics of our patients by providing summary statistics stratified by treatment group. Comparisons between the demographics of the two treatment groups will be made using Fisher's Exact or chi squared tests for categorical variables and using T-test or Wilcoxon rank sum tests for continuous variables, where appropriate. Primary and secondary outcomes will also be compared using treatment-stratified summary statistics, and p-values obtained using the aforementioned statistical tests.

Univariate logistic regression models will be fit using the demographic variables obtained in the study, as well as treatment, to predict patients' primary outcomes. Then, one multivariate model will be constructed for each primary outcome with treatment included as a predictor and an AIC-based stepwise forward model selection procedure dictating what other variables to include into the model. Univariate generalized linear models using treatment group as the predictor variable will also be examined for the secondary outcomes.

Data will be reported using the CONsolidated Standards Of Reporting Trials (CONSORT) guidelines and standard flow diagram.

Breaking the Blind

A subject's treatment assignment will not be broken until the end of the study unless medical treatment of the subject is dependent on knowing the treatment the subject received. Should a medical emergency require the blind to be broken the investigator may unblind an individual subject's treatment allocation.

Research Visit Summary:

Baseline visit confirming eligibility with inclusion and exclusion criteria

Basic demographic data will be recorded

Past medical history will be recorded

Pregnancy test (if of child-bearing age)

Urinalysis dipstick to exclude active urinary tract infection

Bladder scan to see how much urine is in the bladder prior to urinary stress test

Pelvic exam with urinary stress test

Bladder scan after voiding to check post-void residual

Three surveys before the procedure

- Female Sexual Function Index
- Incontinence Quality of Life
- Questionnaire for Urinary Incontinence Diagnosis

Blood draw of about 15 mL

Randomization

Injection procedure

Visual analog Scale (VAS) for pain/discomfort associated with the procedure Injector completes Visual analog Scale (VAS) for level of difficulty of procedure

1-Month Telephone Visit

Record any adverse events

Surveys

- Incontinence Quality of Life

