- Questionnaire for Urinary Incontinence Diagnosis
- Patient Global Impression of Improvement

3-Month Visit

Record any adverse events Pelvic exam with cough stress test Surveys

- Female Sexual Function Index
- Incontinence Quality of Life
- Questionnaire for Urinary Incontinence Diagnosis
- Patient Global Impression of Improvement

6-Month Visit

Record any adverse events Pelvic exam with cough stress test Surveys

- Female Sexual Function Index
- Incontinence Quality of Life
- Questionnaire for Urinary Incontinence Diagnosis
- Patient Global Impression of Improvement
- Perception of Monetary Value

\$50 eVoucher for completion of 6-month follow-up visit

Benchmarks for Success

After enrollment of the first 5 subjects, a quality control of the data collected and entry will be performed. Additional quality control will be performed by the PI after every 10 patients. Meticulous recording of adverse events will be performed. If adverse events are frequent and distressing, the project will be halted and data collected to that point will be analyzed.

After enrollment of 25 subjects, preliminary data and adverse events will be analyzed by a Data and Safety Monitoring Board made up of the research team members.

Potential Problems

Potential problems include low or slow enrollment. In addition to screening patients in the clinic, we can also plan on advertising the study via the University of Iowa listserv and/or advertisement materials to other clinics, such a family medicine, internal medicine, and gynecology.

Since this is a new procedure not well-described in the literature, another potential problem may be the learning curve of the procedure. To mitigate this, only two clinicians will serve as the injector, including the PI

and one other fellowship-trained FPMRS specialist. This will allow consistent and standardized procedure methods.

Timetable and Plan For Completing Project

February 2022: set up REDCap database

March 2022: complete IRB application (as of grant submission, the IRB application has been approved pending minor modifications)

June 2022: start screening clinics for eligible patients, enroll subjects

June 2022 - September 2023: enroll patients, collect data

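### Does scoring women who leave early for other SUI treatment on their exit date undermine the 6-month primary outcome?

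*Combined protocol and SAP*

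**What the plan says.** Approach lists a stress test and the PGI-I under the sentence "The primary efficacy aim will be determined by the following outcome measures", and combines them into one definition of success: "a negative CST and a reported PGI-I of 'very much better' or 'much better' 6 months after treatment".

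The follow-up paragraphs under Injection Procedure deal with women who want a different SUI treatment before 6-month follow-up is complete: "they will be exited from the trial and final outcomes will be assessed at that time". They do not list what the exit assessment contains, and Research Visit Summary has no exit visit.

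Statistical Analysis and Data Reporting says: "Primary and secondary outcomes will also be compared using treatment-stratified summary statistics, and p-values obtained using the aforementioned statistical tests". For a binary outcome this means Fisher's "Exact or chi squared tests for categorical variables". The section names no analysis set and has no sentence on exits. It cites CONSORT, which governs reporting and does not define a population.

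Power Analysis assumes 70% v 20%, needs 19 per group, and enrols 25 per group to allow for 20% drop-out.

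**The concern.** Two parts of the plan give two dates for the same outcome: 6 months in Approach, and the exit day for a woman who leaves for other treatment. Wanting another treatment is plausibly related to how well the injection worked, so these women are not a random subset. If a woman happens to be scored a success on the day she leaves, she could enter the 6-month comparison as a success. If "they will be exited from the trial and final outcomes will be assessed at that time" is read with the stress on leaving the trial, she could instead vanish from the denominator.

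With 25 per arm, one woman's classification can carry a p-value across 0.05. A rule chosen after results are known would be open to criticism. Benchmarks for Success adds to the unease, because after 25 subjects "preliminary data and adverse events will be analyzed by a Data and Safety Monitoring Board made up of the research team members".

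**Working it through.** **Inputs from Power Analysis.** Success 70% v 20%, alpha 0.05 (two-sided assumed; the plan does not say), 19 per group as the minimum, 25 per group enrolled.

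**The plan's own figure.** With pooled variance and no continuity correction,
n = [1.960 × √(2 × 0.45 × 0.55) + 1.282 × √(0.7 × 0.3 + 0.2 × 0.8)]² / 0.50² = 18.6, so 19 per group and 38 in all. This reproduces the protocol. Allowing for 20% loss, 50 × 0.8 = 40, which exceeds 38.

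**Assumed inputs.** The documents give no exit rate. Let *p* be true 6-month success, *e* the share of failures who exit, and *q* the share of exits scored as a success that day. Scoring on the exit day gives

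observed rate = p + (1 − p) × e × q.

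Power and type I error below come from exact enumeration of two binomials with 25 per arm, rejecting at p ≤ 0.05. Results are Fisher / uncorrected chi-squared, since the plan allows either test.

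| Scenario | Rates compared | Rejection probability |
|---|---|---|
| 70% v 20%, exits not a success (q = 0) | 0.700 v 0.200 | 0.946 / 0.972 |
| same, e = 0.2 in both arms, q = 0.1 | 0.706 v 0.216 | 0.936 / 0.966 |
| same, e = 0.2 in both arms, q = 0.2 | 0.712 v 0.232 | 0.924 / 0.959 |
| No effect, 20% in both arms, q = 0 | 0.200 v 0.200 | 0.022 / 0.055 |
| same, e = 0.2 v 0.1, q = 0.1 | 0.216 v 0.208 | 0.023 / 0.055 |
| same, e = 0.2 v 0.1, q = 0.2 | 0.232 v 0.216 | 0.023 / 0.057 |

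At the design rates the difference shrinks from 50 to 49 or 48 points, which works against PRP. With no effect and uneven exits the bias is 0.8 or 1.6 points.

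**How often the problem case arises.** It needs a woman with a negative stress test and one of the two best PGI-I answers who nevertheless leaves for other SUI treatment. At e = 0.2 and q = 0.1 the expected numbers are 25 × 0.3 × 0.2 × 0.1 = 0.15 on PRP and 25 × 0.8 × 0.2 × 0.1 = 0.40 on placebo. At q = 0.2 they double, to 0.30 and 0.80.

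**What one such woman can do.**

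- On PRP: 13/25 v 5/25 gives 0.038 / 0.018, and 12/25 v 5/25 gives 0.072 / 0.037, so Fisher crosses 0.05. One step lower, 11/25 v 5/25 gives 0.128 / 0.069, so chi-squared crosses.
- On placebo: moving from 13/25 v 5/25 to 13/25 v 6/25 gives 0.079 / 0.041, so Fisher crosses. Moving from 12/25 v 5/25 to 12/25 v 6/25 gives 0.140 / 0.077, so chi-squared crosses.

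These tables sit on the boundary. At 70% v 20%, taking away one PRP success turns a significant result non-significant in 4.3% (Fisher) or 2.6% (chi-squared) of trials. At 50% v 20% it does so in about 12% or 11%.

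**If exits were dropped instead.** At 70% v 20% with e = 0.2 in both arms, power is 0.919 / 0.945. With no effect and e = 0.2 v 0.1, type I error is 0.034 / 0.055. A single table can still cross: 12/25 v 5/25 (0.072 / 0.037) becomes 12/24 v 5/25 (0.038 / 0.027).

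**The case for a change.** The strongest reply is that the sentence on exits tells staff when to collect data and does not tell the analyst what to do with them. Taken as an analysis rule it contradicts the 6-month definition; taken otherwise it leaves room for exclusion. On either reading a sentence is missing, a close result could turn on it, and members of the research team will have seen preliminary data. Writing the sentence would cost almost nothing.

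Part of this stands. The plan contains no explicit link between the exit assessment and the composite, names no analysis set, and does not say that a stress test is done at exit. A borderline result would be sensitive to one classification.

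The rest is weaker. A specific provision for early leavers reads most naturally as an exception, fixed in advance, to the general 6-month definition. Dropping a woman whose final outcome has just been assessed fits that provision poorly, and nothing instructs it. Sensitivity to one woman is common to any binary comparison of this size, and part of the movement across 0.05 comes from the open choice between Fisher and chi-squared, which is a separate matter. The review after 25 subjects is not said to be by arm. The statement "At the end of the 6 months, subjects will be unblinded" concerns participants at the end of their follow-up and does not show that analysts see results by arm.

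The obvious alternative is not free either. Suppose every exit counts as not a success and 20% of each arm leaves regardless of outcome. The rates become 56% v 16% and power falls to 0.797 / 0.877. If 10% leave, they are 63% v 18%, with power 0.887 / 0.936.

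**Conclusion.** The gap is real but does not need a change to the plan. Followed on its natural reading, the plan gives a sound comparison: at most 0.022 of Fisher power is lost (0.946 to 0.924), and type I error rises by no more than about 0.002 with either test. The composite protects itself. A woman asking for further SUI treatment must report one of the two best PGI-I answers and also be dry on the stress test to count as a success. A PGI-I below that level settles her as a failure even if no stress test was done. Scoring her on the exit day and counting her as not a success will therefore agree for nearly all exits. Either is a defensible choice, and competent analysts would keep her in her assigned arm and show exits in the CONSORT flow diagram that the plan already promises.

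This rests on assumed figures: 20% of failures exiting (20% v 10% in the no-effect case) and 10% to 20% of exits scored as successes. With fewer exits the effect shrinks, and with none it disappears. It would be larger if many women left while dry and much improved, which nothing in the documents suggests. Losses for other reasons are a different question and are not judged here.

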The study population is women aged 18 years or older with stress-predominant urinary incontinence conformed by a positive cough stress test, as well as a higher SUI MESA score over the UUI MESA score. The approximate number of subjects will be 50, based on a power analysis as described below. The length of follow up will be 6 months post injection.

Following approval by the local Institutional Review Board (IRB), subjects will be recruited from the University of Iowa Hospitals and Clinics Urology and Urogynecology Clinics during regularly scheduled appointments. Subjects will be referred to the study by physician referral. This trial will be registered with clinicaltrials.gov prior to any subject enrollment.

Enrollment

Potential participants will be approached in clinic and be given an overview of the study. If they meet the inclusion criteria and none of the exclusion criteria, the research coordinator will initiate the informed consent process. To assure patient privacy during the informed consent process, the discussion will be held in a private room at the clinic, with the door closed. Once the potential participant has ample time to consider the study, they will be asked to sign the written consent form with the consent provider. A copy of the signed consent form will be given to the patient and the original placed in the research record.

Equipment

Using the Arthrex Autologous Conditioned Plasma (ACP) Double Syringe System (Arthrex Inc, Naples, Florida), approximately 15 mL of the subject's venous blood will be collected from the antecubital fossa. The sample, in the ACP system, will be centrifuged in the clinic lab space. A representative from the company may be present for this portion of the procedure to ensure proper use of the centrifuge. However, the company is not funding this study, has not been involved with protocol development and will not be involved in data analysis,

interpretation or publication of results. Centrifuging takes approximately 5 minutes. At the end of the process, approximately 5 mL of the subject's PRP will be separated. The principal investigator (PI) and research staff will be trained on the processing procedure by [name] from the Sport Medicine Clinic and by the company representative, in order to ensure the procedure is performed using standardized and safe methods.

Randomization

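### The early-exit rule ends adverse-event follow-up before 6 months for women who want other SUI treatment; continuing the safety calls would close a small, possibly arm-dependent gap

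*Combined protocol and SAP*

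**What the plan says.** The Specific aims section makes safety one of two primary aims. The Approach section says that it is assessed through adverse events graded by Clavien-Dindo, without giving an observation window. Methodology sets the duration: "The length of follow up will be 6 months post injection". The Research Visit Summary has adverse events recorded at a 1-month telephone visit and at the 3- and 6-month visits.

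The follow-up paragraphs under Injection Procedure cover women who want alternative SUI treatment before 6 months: "they will be exited from the trial and final outcomes will be assessed at that time". No section describes contact after exit.

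Statistical Analysis and Data Reporting compares primary outcomes by arm with Fisher's exact or chi-squared tests and t or Wilcoxon tests. It mentions neither person-time, nor censoring, nor early exit.

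The Power Analysis is written "assuming true response rates of 70% and 20% for treatment and placebo groups, respectively". Response there is the composite in the Approach section (negative stress test and a good PGI-I rating), measured "6 months after treatment". Enrolment is raised to 50 "In order to account for a 20% drop-out rate", with no split by arm.

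**The concern.** Observation of a primary outcome stops at a post-randomisation event, the wish for other treatment. That wish probably follows persisting leakage, which the plan expects more often on placebo. Two things could follow.

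- If placebo women leave more often, they are observed for less time, and raw adverse-event counts lean against PRP.
- Late events in PRP women who fail and leave are not seen, which leans the other way.

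The net direction is unknown. Under Potential Problems the protocol itself describes the procedure as new and little documented, and there are only 25 women per arm. Late safety data on even a few of them have value and cannot be recovered afterwards.

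**Working it through.** **Inputs from the Power Analysis.** Response 70% (PRP) and 20% (placebo); 25 enrolled per arm; 20% drop-out. **From Methodology.** 6 months of follow-up. **Assumed, because the documents give no value.** The share q of non-responders who exit, taken as equal in both arms; the month t of exit; no exits among responders; the adverse-event risk and its timing.

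**The plan's own figure.** Two-sided alpha 0.05, 90% power, pooled variance, no continuity correction:

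n = [1.96·√(2·0.45·0.55) + 1.2816·√(0.7·0.3 + 0.2·0.8)]² / 0.5² = (1.379 + 0.780)² / 0.25 ≈ 18.6, so 19 per arm.

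This agrees with the plan: "a sample of 38 subjects (19 per treatment group) is the minimum number required to have >90% power". Dividing 38 by 0.8 gives 48; the plan enrols 50, of whom 20% is 10 drop-outs.

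**Expected non-responders.** PRP 25 × 0.30 = 7.5; placebo 25 × 0.80 = 20; ratio 2.67. This becomes a ratio of exits only under the equal-q assumption.

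**Woman-months.** Full follow-up is 25 × 6 = 150 per arm. Loss = non-responders × q × (6 − t). With t = 3:

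| q | Exits, PRP / placebo | Total exits | Months lost, PRP | Months lost, placebo | Observed months, placebo ÷ PRP |
|---|---|---|---|---|---|
| 0 | 0 / 0 | 0 | 0 | 0 | 1.00 |
| 10% | 0.75 / 2 | 2.75 | 2.25 (1.5%) | 6 (4%) | 0.975 |
| 25% | 1.875 / 5 | 6.9 | 5.625 (3.75%) | 15 (10%) | 0.935 |
| 36.4% | 2.7 / 7.3 | 10 | 8.2 (5.5%) | 21.8 (14.5%) | 0.904 |
| 50% | 3.75 / 10 | 13.75 | 11.25 (7.5%) | 30 (20%) | 0.865 |

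The 36.4% row is 10 / 27.5: all ten planned drop-outs are exits of this kind. The 50% row goes beyond the drop-out allowance. Timing matters too: at q = 25% the ratio is 0.889 for exit at month 1 and 0.968 for exit at month 4.5.

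**Effect on the adverse-event comparison.** Assume the same true 6-month risk R in both arms and a constant hazard. Risk by month t is r = 1 − (1 − R)^(t/6). Observed risk is R − f·(R − r), where f is the fraction of the arm that exits. For R = 20% and t = 3, r = 1 − √0.8 = 10.56%, so R − r = 9.44 points.

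- q = 25%: PRP 20 − 0.075 × 9.44 = 19.3%; placebo 20 − 0.20 × 9.44 = 18.1%. Gap 1.2 points, or 0.3 women of 25.
- All ten drop-outs: PRP 20 − 0.109 × 9.44 = 19.0%; placebo 20 − 0.291 × 9.44 = 17.3%. Gap 1.7 points, or 0.4 women.

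**Sensitivity at q = 25%.** With exit at month 3, R = 10% gives a gap of 0.15 women and R = 40% gives 0.55. With R = 20% and exit at month 1 the gap is (18.77 − 16.73)% × 25 = 0.5 women. With R = 40% and exit at month 1 it is (37.61 − 33.63)% × 25 = 1.0. If events cluster soon after the injection, the gap goes towards zero.

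**After the change.** Apart from true loss to follow-up, observation is 150 against 150 woman-months. The sample size does not change.

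**The case against.** The strongest reply is that the plan contains no exit rates. A reader might infer from 70% and 20% that placebo women will leave far more often, so that the safety comparison is certain to rest on unequal times. The documents do not support that. The rates are expected success on a 6-month composite, and failing it at month 6 is not the same as asking for other treatment earlier. The plan also discourages leaving: standard of care is offered after the final visit, unblinding comes at 6 months, and the voucher depends on the 6-month visit. This stands, and the imbalance is a possibility, not a finding.

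A reader might also infer that safety data on women who leave are absent. They are not. Outcomes are assessed at exit and all adverse events are to be recorded, so events up to exit are captured. Observation time to exit could be computed from trial records. Only later events are lost. Nor do the documents say that other treatment would be an operation at the injected site; the Significance section also lists non-surgical options.

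Finally, stopping safety observation when another treatment starts is defensible. Later events are confounded with that treatment, and if exits are commoner on placebo, an undivided 6-month count would charge the other treatment's harms mainly to placebo. This also stands. It is a reason to report two windows, not a reason to stop collecting.

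**Conclusion.** The point holds as a gap in the plan with a cheap remedy. As written, a primary outcome can lose follow-up through an event probably tied to non-response, and the analysis makes no allowance for it. Whether placebo loses more depends on PRP working as assumed and on non-responders leaving at similar rates in both arms.

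The likely effect is small: under one woman per arm at a 20% risk, constant hazard and exit at month 3, with exits kept within the 20% drop-out. It reaches about one woman only under harsher assumptions, such as a 40% risk with exit at month 1. Using the drop-out figure as a ceiling is itself an assumption, since the plan does not say whether these exits count towards it.

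The documents do not support the inference that PRP would look falsely safe. The mechanism that can be quantified makes PRP look slightly worse, while missed late events in PRP women who leave work the other way by an unknown amount. The main loss is late safety information.

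**What to change.** Amend the exit sentence. The efficacy assessment at exit stays as written. Adverse events continue to be collected by telephone at whichever scheduled time points remain (1, 3 and 6 months after injection), unless the woman withdraws consent. Record the date of each event and the date on which any other SUI treatment starts.

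In the analysis section, state that adverse events will be reported by arm over two windows: up to the start of other treatment, and over the full 6 months. Show events after other treatment separately, and give woman-months of observation per arm.

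The cost is a sentence in the protocol and consent form, a short addition to the analysis text, and one or two calls per exiting woman by staff who already make the 1-month call. The drawback is that events after other treatment are confounded with it and cannot be read as effects of the injection, so they must not be pooled with the rest. Access to other treatment and the efficacy endpoint are unaffected.

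### Does the claim of more than 90% power with 38 subjects fail because the test is left open and the placebo rate is for the stress test alone?

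*Combined protocol and SAP*

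**What the plan says.** The Power Analysis section sets a target of at least 90% power, "assuming true response rates of 70% and 20% for treatment and placebo groups, respectively". It continues "Using an unadjusted alpha of 0.05" and concludes that "a sample of 38 subjects (19 per treatment group) is the minimum number required to have >90% power to detect a difference". It names neither the test nor whether it is one- or two-sided. Allowing for 20% dropout, 50 patients are to be enrolled, 25 per arm.

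The two rates are sourced differently. The 70% "was chosen based on prior studies of PRP, as well as urethral bulking procedures", with no statement of the endpoint behind it. The 20% rests on "prior urethral bulking studies showing a 20% rate of negative CST after placebo".

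In the Approach section, treatment success "will be defined as a negative CST and a reported PGI-I of" much or very much better at 6 months, so both components are required.

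Statistical Analysis and Data Reporting lists "Fisher's Exact or chi squared tests for categorical variables", to be chosen as fits the data, and applies the same set of tests to the primary and secondary outcomes. It gives no rule for choosing between the two.

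**The concern.** The size of 50 patients rests on this one power statement, and two things seem to undercut it.

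First, the two tests on offer do not have the same power in samples this small. Fisher's test is conservative, and at 70% against 20% with 19 per arm it falls short of 90%. The dropout allowance does not repair that, because Fisher's test first exceeds 90% at 23 per arm while the plan expects about 20. The open choice could also decide a borderline result: with 20 per arm, 12 against 5 successes gives p = 0.025 by uncorrected chi-squared and p = 0.054 by Fisher's test.

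Second, the trial tests a composite, but the placebo input describes one component. Adding a second requirement can only lower a success rate. If both inputs were CST rates, the true composite rates would be lower in both arms and the difference between them smaller.

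If either point held, the trial would have less power than it claims, and a null result could be read as stronger evidence of no effect than it is.

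**Working it through.** **Inputs.** From Power Analysis: p1 = 0.70, p2 = 0.20, alpha 0.05, target power 0.90, 20% dropout, 50 enrolled. From Randomization: equal allocation. Two-sided testing is assumed, because sidedness is not stated.

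**Step 1: reproduce the stated size.** The pooled normal formula, which corresponds to the uncorrected chi-squared test, is

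n per arm = [z(0.975)·√(2·p̄·(1−p̄)) + z(0.90)·√(p1(1−p1) + p2(1−p2))]² / (p1−p2)²

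with p̄ = (0.70 + 0.20)/2 = 0.45. Then:

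- 1.960 × √(2 × 0.45 × 0.55) = 1.960 × 0.7036 = 1.379
- 1.2816 × √(0.21 + 0.16) = 1.2816 × 0.6083 = 0.780
- (1.379 + 0.780)² / 0.25 = 18.64 with unrounded terms, rounded up to 19 per arm, 38 in total

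The plan's figure is reproduced. After dropout, 50 × 0.8 = 40, or 20 per arm.

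**Step 2: exact power by test.** Summing binomial probabilities over all outcome pairs at 70% v 20%, two-sided 0.05:

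| Per arm | Uncorrected chi-squared | Fisher's exact |
|---|---|---|
| 19 | 90.7% | 85.2% |
| 20 | 90.8% | 84.6% |
| 22 | 93.9% | 89.0% |
| 23 | 95.3% | 91.3% |
| 25 | 97.2% | 94.6% |

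**Step 3: power under the usual selection rule.** Assume the common convention: Fisher's test if any expected count is below 5, otherwise chi-squared. At 19 per arm the expected counts under the planning rates are 19 × 0.45 = 8.6 successes and 19 × 0.55 = 10.5 failures in each arm, so chi-squared is chosen. Applying the rule to every possible outcome pair gives:

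- 19 per arm: power 90.7%, with Fisher's test used in 0.18% of trials
- 20 per arm: power 90.8%, with Fisher's test used in 0.07% of trials

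**Step 4: correct the placebo rate alone.** A woman who meets the composite has a negative CST, so in the same women the composite rate cannot exceed the CST rate. Holding PRP at 70% with 20 per arm:

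| Placebo composite rate (assumed) | Chi-squared | Fisher's exact |
|---|---|---|
| 20% | 90.8% | 84.6% |
| 15% | 96.3% | 93.1% |
| 10% | 99.0% | 97.9% |

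Power rises, and at 15% or below even Fisher's test clears 90%.

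**Step 5: what it takes to lower power.** Suppose instead that the 70% is also a CST rate and that the same share q of CST-negative women in each arm report PGI-I 1 or 2. Both are assumptions. With 20 per arm:

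| q | Composite rates | Chi-squared | Fisher's exact |
|---|---|---|---|
| 0.9 | 63% v 18% | 85% | 77% |
| 0.8 | 56% v 16% | 79% | 69% |
| 0.7 | 49% v 14% | 70% | 58% |

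The direction therefore turns on what the 70% measures, which the plan does not say.

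**The case for a change.** The strongest case for a change is that the figure and the analysis are not tied together in writing. No selection rule is stated, so the expected-count convention in Step 3 is supplied by the reader. An analyst who used Fisher's test whatever the counts would still be within the plan, would have about 85% power, and would need 46 evaluable women (46/0.8 = 57.5, so 58 enrolled) to pass 90%. The 12 v 5 example shows that the choice can matter. Other defensible analyses spread on both sides of 90% at 19 per arm: 93.0% for a likelihood-ratio test and 87.3% for a Wald test from the univariate logistic model, and 81.8% for a Yates-corrected chi-squared test. One sentence would settle it, at no cost in patients.

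The facts in this stand: the test, its sidedness and the endpoint behind the 70% are not stated. What does not stand is the inference that the stated power is missed. Naming Fisher's test first in a list does not give it priority, and the list also covers demographic variables, where small counts are more likely and Fisher's test has its natural use. If the omission were filled by naming the uncorrected chi-squared test, no stated figure would change. The PRP rate may be optimistic for a composite, but the Significance section reports success in up to 80% of patients in small PRP series, so 70% does not exceed the range that the plan itself cites.

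**Conclusion.** No change follows. The 38 is correctly calculated. Power exceeds 90% at both 19 and 20 per arm under the uncorrected chi-squared test, and equally under the ordinary reading of the two-test wording. The shortfall of about 6 percentage points (85.2% and 84.6%) arises only if Fisher's test is used whatever the counts, which the plan does not say.

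The one documented endpoint mismatch, the CST-only placebo rate, is conservative: 70% v 15% at 20 per arm gives 96% by chi-squared and 93% by Fisher's test. Figures from 85% down to 58% depend on reading the 70% as a CST-only rate, for which the documents give no support either way.

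This conclusion assumes a two-sided test and a cutoff at expected counts below 5, and it takes the 70% as the intended composite rate. What remains is a gap in specification: test, sidedness and the labelling of the two rates. Analysts would fill it sensibly, and doing so would alter neither the sample size nor the stated power.
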